#### 8.3.5. ADVERSE EVENT REPORTING

All adverse events will be recorded and collated by the investigators. The data will be collected from each participants data sheet that is completed at each of their study visits. The incidence of expected adverse events will be reported in the published data along with the occurrence and incidence of unexpected adverse events.

---

#### 8.3.6. SERIOUS ADVERSE EVENT REPORTING

The study clinician will immediately report to the Women's and Children's Health Network Human Research Ethics Committee (HREC) any serious adverse event, whether or not considered study intervention related, including those listed in the protocol or investigator brochure and must include an assessment of whether there is a reasonable possibility that the study intervention caused the event. Study endpoints that are serious adverse events (e.g., all-cause mortality) must be reported in accordance with the protocol unless there is evidence suggesting a causal relationship between the study intervention and the event (e.g., death from anaphylaxis). In that case, the investigator must immediately report the event to the TGA.

All serious adverse events (SAEs) will be followed until satisfactory resolution or until the site investigator deems the event to be chronic or the participant is stable. Other supporting documentation of the event may be requested by the therapeutic substances committee and will be provided as soon as possible.

---

### 8.3.7. REPORTING EVENTS TO PARTICIPANTS

Participants will be invited to inquire about the results of the trial and incidence and nature of adverse effects after the completion of the trial.

---

### 8.3.8. EVENTS OF SPECIAL INTEREST

Not applicable

---

### 8.3.9. REPORTING OF PREGNANCY

If patients are found to be pregnant prior to undergoing spinal fusion surgery they will be excluded from the trial as their surgery date will be postponed until following completion of their pregnancy. If a patient is found to be pregnant from any time after their surgical date they will continue to be included in the trial and their data collected in the usual fashion.

---

## 8.4. UNANTICIPATED PROBLEMS

---

### 8.4.1. DEFINITION OF UNANTICIPATED PROBLEMS (UP)

Unanticipated problems involving risks to participants or others include, in general, any incident, experience, or outcome that meets all of the following criteria:

- Unexpected in terms of nature, severity, or frequency given
  - (a) the research procedures that are described in the protocol-related documents, such as the Institutional Review Board (IRB)-approved research protocol and informed consent document; and
  - (b) the characteristics of the participant population being studied;
- Related or possibly related to participation in the research; and
- Suggests that the research places participants or others at a greater risk of harm (including physical, psychological, economic, or social harm) than was previously known or recognised.

---

### 8.4.2. UNANTICIPATED PROBLEM REPORTING

The investigator will report unanticipated problems (UPs) to the reviewing Drug and Therapeutics Committee (DTC) and lead principal investigator. The UP report will include the following information:

- Protocol identifying information: protocol title and number, PI's name, and the project number;
- A detailed description of the event, incident, experience, or outcome;
- An explanation of the basis for determining that the event, incident, experience, or outcome represents an UP;
- A description of any changes to the protocol or other corrective actions that have been taken or are proposed in response to the UP.

To satisfy the requirement for prompt reporting, UPs will be reported using the following timeline:

- UPs that are serious adverse events (SAEs) will be reported to the HREC within 1 week of the investigator becoming aware of the event.
- Any other UP will be reported to the DTC within 1 month of the investigator becoming aware of the problem.

### 8.4.3. REPORTING UNANTICIPATED PROBLEMS TO PARTICIPANTS

Participants will be invited to inquire about the results of the trial and incidence and nature of unanticipated problems after the completion of the trial.

## 9. STATISTICAL CONSIDERATIONS

### 9.1. STATISTICAL HYPOTHESES

- Primary Efficacy Endpoint(s):
  - Incidence of severe anaemia (Hb <100g/L) at time of discharge from hospital or 7 days postoperatively (whichever is sooner)
  - This trial is designed to demonstrate superiority of IV iron therapy over traditional oral iron therapy.
- Secondary Efficacy Endpoint(s):
  - Incidence of blood transfusion
  - Length of stay
  - Haemoglobin concentration and incidence of anaemia (Hb <120g/L) at 3 weeks postoperatively
  - Haemoglobin concentration and incidence of anaemia (Hb <120g/L) and incidence of iron deficiency (ferritin <30mcg/L) at 9 weeks postoperatively
  - Quality of functional recovery from surgery as measured by the SRS 30 at 9 weeks postoperatively

### 9.2. SAMPLE SIZE DETERMINATION

The null hypothesis states that there is no difference between oral and IV iron therapy in the incidence of severe anaemia at the time of discharge following elective spinal fusion surgery. The primary outcome measure is the Incidence of severe anaemia (Hb <100g/L) at discharge from hospital.

Previous audit of 16 spine patients demonstrated a mean discharge Hb of 96g/L, with a standard deviation of 15.2. Haematocrit was not recorded.

Intravenous iron sucrose has been proven to increase Hb in adults with iron deficiency anaemia of various aetiologies that is non-responsive to oral iron by up to 50% (85.4g/L to 121 g/L) .

Whilst the figures for paediatric surgical patients' responsiveness to IV iron are not known (hence the development of the proposed study); it has been postulated that this may be likely to be similar to adults. Thus these preexisting findings in adults allow for an extrapolation of data to enable power calculation for the proposed study. Namely, that of the of patients being discharged with severe anaemia (Hb <10 g/dL) after spinal surgery - which currently number 68% of patients - should be able to be halved (50% decrease) through judicious and appropriate IV iron therapy.

In view of the lack of previously defined population characteristics, power calculations have been done using:

- a two study group design (Population rates of Discharge Hb<100 of 68.75% observed previously, compared to the expected post iron-infusion rates of Discharge Hb<100 of 34.38%, a figure chosen for reasons outlined above.)
- Further, while data will be collected in a continuous manner, it will be analysed as dichotomous, binomial data (two outcomes only: Hb >10 g/dL or Hb <10g/dL.) to reduce the number of patients required for the study.
- Assumption of alpha of 0.05, as per current medical research convention 
- Assumption of power (1-beta) of 0.8 as per current medical research convention 

This will result in an expected sample size of approximately 14 patients in the treatment group.

This figure has been reached using the following equation (fig. 1), which was selected to meet the above criteria . The calculation was performed using the on-line tool at <http://clincalc.com/stats/samplesize.aspx>.

This power calculation remains a guide, and will be subject to formal review by a statistician. Further recruitment may be required in the event of patient drop-out, the rates of which are difficult to predict. Anticipating a 10% attrition rate we will aim to recruit 34 patients (17 in each treatment arm).

$$N = \frac{p_0q_0 \left\{ z_{1-\alpha/2} + z_{1-\beta} \sqrt{\frac{p_1q_1}{p_0q_0}} \right\}^2}{(p_1 - p_0)^2}$$

$$q_0 = 1 - p_0$$

$$q_1 = 1 - p_1$$

$$N = \frac{0.6875 * 0.3125 \left\{ 1.96 + 0.84 \sqrt{\frac{0.3438 * 0.6562}{0.6875 * 0.3125}} \right\}^2}{(0.3438 - 0.6875)^2}$$

$$N = 14$$

$p_0$  = proportion (incidence) of population  
 $p_1$  = proportion (incidence) of study group  
 $N$  = sample size for study group  
 $\alpha$  = probability of type I error (usually 0.05)  
 $\beta$  = probability of type II error (usually 0.2)  
 $z$  = critical Z value for a given  $\alpha$  or  $\beta$

Figure 1.

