1.2. SCHEMA

**1.3. SCHEDULE OF ACTIVITIES (SOA)**

Procedures	Enrolment/ Visit 1, Day -42 (+/- 14 days)	Group identification, Day -35 (+/- 14 days)	Study Visit 2, Day -28 (+/- 7 days)	Day Before Surgery Day -1	Day of Surgery Day 0	In hospital Days 1-5	Discharge Day 5 (+/- 2days)	Study Visit 3 Day 21 (+/- 7 days)	Final Study Visit 4 Day 63 (+/- 14 days )
Informed consent	X								
Demographics	X								
Medical history	X								
Baseline screening bloods	X								
Interpretation of bloods		X							
Randomization		X							
Administer study intervention - Intravenous iron therapy (IV arm only)			X						
Administer study intervention - Oral iron therapy (Oral arm only)		X-----X							
Vital signs	X		X		X	X	X		X
Height	X								X
Weight	X								X
SRS 30 Questionnaire	X								X
Full Blood Exam	X				X	X	X	X	X
Iron Studies	X				X				X
Electrolytes (“ELC”)	X				X				X
Vitamin D Level	X								
Surgical data - ASA, spinal levels, blood loss, cell salvage volume					X				
Transfusion volume					X	X	X		
Oral Iron Compliance Questionnaire						X			
Adverse event review and evaluation	X	X-----X							X
Data Entry	X	X	X		X	X	X	X	X

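### Dichotomising discharge haemoglobin is justified as needing fewer patients, but it needs about one and a half times as many

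*Protocol*

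**What the plan says.** Protocol section 9.2 gives the audit result, "Previous audit of 16 spine patients demonstrated a mean discharge Hb of 96g/L, with a standard deviation of 15.2", and two rates for planning: "Population rates of Discharge Hb<100 of 68.75% observed previously", against "expected post iron-infusion rates of Discharge Hb<100 of 34.38"%. It then says that the continuously collected Hb will be split at 10 g/dL: "it will be analysed as dichotomous, binomial data (two outcomes only: Hb >10 g/dL or Hb <10g/dL.) to reduce the number of patients required". The error rates are "Assumption of alpha of 0.05, as per current medical research convention" and "Assumption of power (1-beta) of 0.8 as per current medical research convention". Figure 1 of that section yields 14 for the treatment group, and the target with 10% attrition is 17 per arm, 34 in all.

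Section 3 gives a separate reason for the endpoint: severe anaemia matters clinically and is easy to measure. Sections 3 and 9.1 list Hb concentration as an endpoint only at the later postoperative visits, not at discharge. The Schedule of Activities (section 1.3) has a "Full Blood Exam" at enrolment and at discharge, so both values will be on file.

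**The concern.** Splitting a continuous measurement at a threshold discards how far each patient lies from it. For the same underlying effect, a test on the split data therefore needs more patients. Section 9.2 states the opposite as its reason for the analysis, and shows no continuous calculation to support it although it prints a mean and an SD.

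The choice matters because the trial is small. Sections 2.2 and 2.3.3 say that a failure to show superiority would support continued use of oral iron. If the planned comparison has about an even chance of missing the effect it was designed for, a false negative would be read as guidance for practice.

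**Working it through.** **Inputs.** All are from section 9.2: p0 = 0.6875, p1 = 0.34375 (printed as 34.38%), two-sided alpha 0.05 (z = 1.96 in Figure 1), power 0.80 (z = 0.84), audit mean 96 g/L, SD 15.2 g/L, 17 per arm, 10% attrition. Normality of Hb with a common SD is my assumption.

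**1. The protocol's own figure.** Figure 1 is N = p0q0{1.96 + 0.84√(p1q1/p0q0)}² / (p1 − p0)². With p0q0 = 0.2148 and p1q1 = 0.2256 it gives 14.47, printed as 14. Rounding up, 15/0.9 = 16.7, so 17. The formula tests one sample against a fixed rate. Section 4.1 randomises two concurrent arms.

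**2. Two arms, binary.** With p̄ = (p0 + p1)/2 = 0.5156:

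n = {1.96√(2p̄q̄) + 0.84√(p0q0 + p1q1)}² / (p0 − p1)² = 31.97, so **32 per arm** (38 with continuity correction).

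**3. Two arms, continuous, same effect.** The rates imply a shift of Φ⁻¹(0.6875) − Φ⁻¹(0.34375) = 0.489 + 0.402 = 0.891 SD, or 13.5 g/L at SD 15.2.

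n = 2(1.96 + 0.84)²/0.891² ≈ 19.8, so 20 per arm; the t-test needs 20.8, so **21 per arm**.

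The ratio is 32/21 ≈ 1.5 by t-test and 32/20 = 1.6 by the normal approximation. Because the rates fix the effect in SD units, this comparison does not depend on the value of the SD.

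**4. Same comparison with the one-sample logic.** Continuous (2.80/0.891)² = 9.9, against 14.5 binary. The direction is unchanged, so the small N is due to the formula and not to the split.

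**5. The other anchor.** Under normality, mean 96 and SD 15.2 put Φ(4/15.2) = 60.4% below 100 g/L, not 68.75%. To reach 34.38% the mean must rise to 100 + 15.2 × 0.402 = 106.1, a shift of 10.1 g/L or 0.665 SD. The t-test then needs 36.4, so **37 per arm**; the binary comparison (60.4% against 34.38%) needs **57 per arm**. Comparisons must stay within one anchor.

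**6. Power at the planned size.** 17 × 0.9 = 15.3, so about 15 per arm remain after attrition.

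| Analysis | 17 per arm | 15 per arm |
|---|---|---|
| Binary, normal approximation, rate anchor | 52% | 47% |
| Binary, Fisher's exact test, rate anchor | 41% | 31% |
| t-test on Hb, rate anchor | 71% | 65% |
| Binary, normal approximation, audit-mean anchor | 32% | 29% |
| t-test on Hb, audit-mean anchor | 47% | 42% |

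**7. Adjustment for enrolment Hb.** ANCOVA raises the standardised effect to d/√(1 − r²), where r is the correlation between enrolment and discharge Hb. The protocol gives no r, so 0 to 0.6 is an assumed range.

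| r | Rate anchor, 17 per arm | Audit-mean anchor, 17 per arm |
|---|---|---|
| 0 | 71% | 47% |
| 0.3 | 75% | 50% |
| 0.6 | 88% | 65% |

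**The case against.** The strongest reply is that the endpoint does not depend on the faulty clause. Section 3 defends Hb below 100 g/L on clinical grounds, and incidence is the primary endpoint and the null hypothesis throughout. A binary endpoint with a correct two-arm sample size would be valid. Section 9.2 also calls its calculation a guide, subject to a statistician's review. This stands: it protects the endpoint, but not the stated reason for analysing it this way.

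Four stronger readings are tempting and are not supported.

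- **Continuous Hb should replace the primary endpoint.** That would change the trial's question from incidence to mean concentration. It is a trade-off, not the correction of an error.
- **A baseline-adjusted analysis would recover most of the lost power.** That holds only on the rate-based anchor with a fairly high correlation. Enrolment Hb is taken about six weeks before surgery. Iron treatment, blood loss, cell salvage and any transfusion come in between, and entry criteria narrow the baseline range. A correlation below 0.3 is plausible.
- **The plan wrongly leaves baseline Hb unused.** Section 9.4 defers analysis methods to a biostatistician, and covariate adjustment can properly be settled in a statistical analysis plan.
- **Transfused patients need a special score.** Using the last Hb before transfusion would give a patient transfused in theatre the induction value. Ranking transfused patients lowest does not fit an ANCOVA in g/L. Neither belongs in this fix.

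Nor is the cut's position near the audit mean the fault; a central cut loses the least.

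**Conclusion.** The efficiency rationale in section 9.2 is wrong in direction. Like for like, dichotomising needs about 1.5 to 1.6 times the patients: 32 against 21 per arm on the protocol's rates, 57 against 37 on the audit mean. The N of 14 is produced by a one-sample formula.

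For the protocol's own rates, the planned binary comparison has 52% power at 17 per arm (41% by Fisher's exact test) and 47% (31%) at 15 per arm, against a stated 80%. Analysing Hb as continuous helps but does not by itself reach 80% at either size on either anchor.

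The sample-size ratio rests on approximate normality and a common SD. The g/L figures and the audit-mean results also rest on an SD from 16 patients (95% interval about 11.2 to 23.5). The adjusted power figures rest on a correlation that the protocol does not supply.

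**What to change.** 1. In section 9.2, delete the statement that dichotomising reduces the number of patients, and rest the Hb <100 g/L endpoint on the clinical reason in section 3.
2. State the power that 17 per arm, and about 15 after attrition, gives in a two-arm comparison of proportions.
3. Add discharge Hb concentration to sections 3 and 9.1 as the first-named key supportive analysis, by ANCOVA with enrolment Hb as covariate.
4. Say that the gain from adjustment depends on an unknown correlation. Give the range for r from 0 to 0.6 at 17 per arm (71% to 88% on the rate-based anchor, 47% to 65% on the audit mean), and say that it does not reliably restore 80%.

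The cost is a wording amendment, which the Statement of Compliance sends to the Ethics Committee, plus one more analysis and a less favourable stated power. These changes need no further data. Keeping 80% power for the binary endpoint would be a separate decision to enlarge the trial: 32 evaluable per arm, or 32/0.9 = 35.6, so 36 per arm with 10% attrition.

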## 2. INTRODUCTION

### 2.1. STUDY RATIONALE

Posterior spinal fusion is considered major elective surgery which is associated with significant intra operative blood loss and post operative anaemia. A retrospective audit at our institution in 2016 has demonstrated that a significant number of patients were presenting for surgery with anaemia (Hb <120g/L) and over 60% of all spinal fusion patients were being discharged from hospital with severe anaemia (Hb <100g/L).

While preoperative optimisation of red cell mass is considered standard practice in the adult perioperative setting there have been few studies to assess its application in paediatric surgery. At the present time there is little preoperative screening in place for systemically well paediatric patients. Until recently patients at our institution were not undergoing routine screening bloods until the night before surgery preventing any preoperative treatment of iron deficiency or anaemia. The perioperative patient who is found to be iron deficient presents a unique challenge to surgeons and anaesthetists who are faced with balancing the desire to provide the best preoperative optimisation without delaying surgery whenever possible. Therefore this study seeks to answer the valuable question of how to best optimise our patient's iron stores in the limited pre-operative period. We aim to determine whether oral iron or intravenous iron is more effective where there is only 4-6 weeks available to achieve adequate replacement of the patients iron stores.

This study aims to assess the efficacy of preoperative screening and treatment of iron deficiency with either oral iron (ferrous sulphate liquid or ferrous fumarate tablets) or intravenous ferric carboxymaltose iron therapy in the paediatric perioperative patient.

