### 2.3.3. ASSESSMENT OF POTENTIAL RISKS AND BENEFITS

Preoperative optimisation of iron stores is an important part of minimising the risk of exposing our patients to a blood transfusion and reducing the burden of post operative anaemia. At the present time there is little preoperative screening in place for systemically well paediatric patients. Until recently patients were not undergoing routine screening bloods until the night before surgery preventing any preoperative treatment of iron deficiency or anaemia. In paediatric medicine oral iron is commonly used as first line therapy to replenish iron stores in those patients who are found to be iron deficient. Oral iron is cheap, relatively safe and easy to administer to children. However, oral iron therapy is often poorly tolerated due to side effects resulting in poor compliance and it is often ineffective even when taken regularly. This study aims to demonstrate that IV ferric carboxymaltose is superior to oral iron therapy in the correction of preoperative iron deficiency and prevention of severe post operative anaemia.

We feel the risks involved in this study are outweighed by the benefits to future patients that can be achieved through effective preoperative iron replacement. If IV ferric carboxymaltose is found to be superior to oral iron therapy then it maybe that the additional cost and risk of the IV formulation can be justified for the management of preoperative iron deficiency in

paediatric patients. If IV ferric carboxymaltose is not found to be superior to oral iron supplementation then this trial will support the continued use of oral iron and it may be possible to avoid the unnecessary cost and inconvenience of an intravenous iron infusion.

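### Section 9.2 sizes a two-arm comparison with a one-sample formula, so 17 per arm gives roughly 41–56% power on the protocol's own rates, not 80%

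*Protocol*

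**What the plan says.** Section 4.1 describes a randomised superiority trial with concurrent oral and IV iron arms of 17 each. The null hypothesis, repeated in section 9.2, is no difference between those arms in severe anaemia at discharge.

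Section 9.2 describes the calculation as "a two study group design (Population rates of Discharge Hb<100 of 68.75% observed previously, compared to the expected post iron-infusion rates" and takes the IV rate as 34.38%, half of the audit figure. It adds "Assumption of alpha of 0.05, as per current medical research convention" and "Assumption of power (1-beta) of 0.8 as per current medical research convention". The result is "This will result in an expected sample size of approximately 14 patients in the treatment group", and then "Anticipating a 10% attrition rate we will aim to recruit 34 patients (17 in each treatment arm". The key to Figure 1 defines p0 as the incidence in the population, p1 as the incidence in the study group, and N as the size of the study group. The section calls the calculation a guide that a statistician will review.

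Section 2.3.3 says in advance how a negative result will be read: if IV iron "is not found to be superior to oral iron supplementation then this trial will support the continued use of oral iron".

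**The concern.** The formula and the design do not match. Figure 1 has a single sample size and treats 68.75% as a constant. In the trial, the oral arm's rate will be estimated from about as few patients as the IV arm's, so the difference between arms carries two sampling errors.

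The stakes come from section 2.3.3. If power is near one half, a true halving of severe anaemia would be missed about as often as it is found. Each miss would then be reported as support for oral iron.

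**Working it through.** **Inputs, all from section 9.2:** p0 = 0.6875; p1 = 0.3438; z for alpha = 1.96 (two-sided, as in the worked equation); z for power = 0.84; difference d = 0.3437, d² = 0.1181; p0q0 = 0.2148; p1q1 = 0.2256.

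**1. Reproduce the protocol's figure (one-sample).**

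N = p0q0 × [1.96 + 0.84 × √(p1q1/p0q0)]² / d² = 0.2148 × [1.96 + 0.84 × √(0.2256/0.2148)]² / 0.1181 = 14.47.

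This matches the stated 14. Rounded up it is 15, and 15/0.9 = 16.7, which gives the planned 17. So the formula in use is confirmed, and 17 recruited corresponds to about 15 evaluable (17 × 0.9 = 15.3).

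**2. Two-sample requirement on the same inputs.**

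Mean rate p̄ = (0.6875 + 0.3438)/2 = 0.5157, so 2p̄(1 − p̄) = 0.4995. The sum of the two variances is 0.2148 + 0.2256 = 0.4404.

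n per arm = [1.96 × √0.4995 + 0.84 × √0.4404]² / 0.1181 = 32 after rounding up (31.98 with unrounded z values).

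With a continuity correction it is 38. With 10% attrition, 32 becomes 32/0.9 = 35.6, or 36 per arm.

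**3. Power of the planned trial (pooled z).**

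At n = 17, the standard error under the null is √(0.4995/17) = 0.1714 and under the alternative √(0.4404/17) = 0.1610. Power = Φ[(0.3437 − 1.96 × 0.1714)/0.1610] = Φ(0.048) = 52%.

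The exact figures below come from enumerating all binomial outcomes at 68.75% v 34.38%, two-sided 0.05:

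| Evaluable per arm | Fisher exact | Pooled z | Chi-square (exact power) |
|---|---|---|---|
| 17 | 41% | 52% | 56% |
| 15 | 31% | 47% | 46% |

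Other standard choices at 17 per arm run from 37.5% (continuity-corrected) to 64.9% (one-sided 0.05). None reaches 80%.

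**4. What 17 per arm can detect.** Against 68.75%, 80% power by chi-square needs an IV rate of about 23%, a difference of about 46 points. At the planned rates the expected 95% CI half-width is 1.96 × 0.1610 = 0.316, about 32 percentage points.

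**5. Sensitivity to the control rate.** 68.75% equals 11/16, which fits the audit of 16 patients. The exact 95% CI for 11/16 is 41% to 89%. Chi-square power at 17 per arm, with assumed rates:

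| Oral rate | IV rate | Power |
|---|---|---|
| 50% | 34.38% | 16% |
| 60% | 34.38% | 35% |
| 68.75% | 34.38% | 56% |
| 80% | 40% | 70% |
| 80% | 34.38% | 81% |

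**The case against.** The best defence is that the protocol calls the calculation a guide awaiting statistical review and openly describes the halving as an extrapolation. That is fair as to the effect size: a target effect is a design choice. It does not rescue the formula, because 34 patients are fixed in the synopsis, in section 4.1 and in section 9.2. The further recruitment that section 9.2 mentions is tied to drop-out.

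A second defence is that section 7.2 replaces treated patients who withdraw, so 17 evaluable per arm may be reached. This stands, and it is why the result is given at both 17 and 15. It does not bring power near 80%.

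Some stronger readings are tempting, but the documents do not support them:

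- *That alpha 0.05 also fails.* The test sets the type I error, not the sample-size formula. At 17 per arm with 68.75% in both arms, the exact size is 4.7% (chi-square) or 2.0% (Fisher).
- *That the audit rate must overstate the oral-arm rate, so power is certainly lower still.* Section 2.1 says "patients at our institution were not undergoing routine screening bloods until the night before surgery preventing any preoperative treatment of iron deficiency or anaemia", which describes past institutional practice and makes it plausible, but does not establish, that the 16 audit patients were untreated. Oral iron could lower the rate. Selecting iron-deficient children could raise it, since section 2.2 reports iron-deficient films in at most 30% of audited patients. The direction is unknown.
- *That section 2.2 repeats the faulty inference.* Its sentence depends on oral iron being found as effective, which is a different condition from failing to show superiority.
- *That rounding 14.47 down, or describing a rise from 85.4 to 121 g/L (42%) as up to 50%, produces the shortfall.* Neither does. Planning for 17 already covers 15, and the power figures take the protocol's two rates as given.

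**Conclusion.** The point holds. The stated 80% power belongs to a comparison with a fixed rate, which this trial does not make. For the randomised comparison it does make, power is about 41–56% with 17 evaluable per arm and 31–47% with 15. Reaching 80% needs 32 evaluable per arm, 64 in total against 34 planned.

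These figures rest on the protocol's own two rates and two-sided 0.05. The spread reflects the choice of test, which the protocol does not name. A single figure such as 52% should not be read as settled, because it assumes a pooled z test and no attrition. With power of this order, the section 2.3.3 reading of a negative result cannot be sustained.

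**What to change.** - **Section 9.2, formula:** replace Figure 1 with the two-sample formula. Keep 34 if that is what is feasible. Restate the power as the range above, naming the test and the evaluable number per arm, or state the detectable difference instead (at 17 per arm, an IV rate of about 23% for 80% power by chi-square).
- **Section 9.2, control rate:** say that 68.75% is an audit rate, not the rate in iron-deficient children given oral iron. Show power for control rates both below and above it.
- **Section 2.3.3:** replace the statement about a failure to show superiority with wording such as: a non-significant result is inconclusive and will be reported as the risk difference with its 95% confidence interval.
- **No change** is needed to alpha or to section 2.2.

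The cost is a less favourable stated power, which the ethics committee will weigh in a paediatric trial, and a wording amendment that needs its approval under the Statement of Compliance. No patients are added.
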